7.1 TRIAL PROCEDURES

7.2 Trial Procedures

The Trial Flow Chart - Section 6.0 summarizes the trial procedures to be performed at each visit. Individual trial procedures are described in detail below. It may be necessary to perform these procedures at unscheduled time points if deemed clinically necessary by the investigator.

Furthermore, additional evaluations/testing may be deemed necessary by the IND Office and/or Merck for reasons related to subject safety. In some cases, such evaluation/testing may be potentially sensitive in nature (e.g., HIV, Hepatitis C, etc.), and thus local regulations may require that additional informed consent be obtained from the subject. In these cases, such evaluations/testing will be performed in accordance with those regulations.

Subjects found to be LOH negative, or subjects who are LOH positive but do not undergo randomization for any reason (including declining randomization) will not be removed from the study. However, they will only undergo the study procedures described under "Pre-Screening Visit 1" and "Long Term Follow-up" of the Trial Flow Chart - Section 6.0. Their medical care and follow up will be performed by the treating physicians according to institutional standards. All other subjects should follow the trial procedures according to the Trial Flow Chart - Section 6.0.

7.1.1 Administrative Procedures

7.1.1.1 Informed Consent

The Investigator must obtain documented consent from each potential subject prior to participating in a clinical trial.

7.1.1.1.1 General Informed Consent

Consent must be documented by the subject's dated signature or by the subject's legally acceptable representative's dated signature on a consent form along with the dated signature of the person conducting the consent discussion.

The initial informed consent form, any subsequent revised written informed consent form and any written information provided to the subject must receive the IRB/ERC's approval/favorable opinion in advance of use. The subject or his/her legally acceptable representative should be informed in a timely manner if new information becomes available that may be relevant to the subject's willingness to continue participation in the trial. The communication of this information will be provided and documented via a revised consent form or addendum to the original consent form that captures the subject's dated signature or by the subject's legally acceptable representative's dated signature.

Specifics about a trial and the trial population will be added to the consent form template at the protocol level.

The informed consent will adhere to IRB/ERC requirements, applicable laws and regulations and IND Office requirements.

7.1.1.2 LOH evaluation

LOH evaluation will be performed in a CLIA certified lab in an archival tissue specimen obtained within 12 months prior to enrollment, or in a newly obtained oral tissue specimen. Subjects do not need to meet the eligibility criteria described in sections 5.1.2 and 5.1.3 to have their tissue evaluated for LOH. LOH will be evaluated in the IEN, using peripheral blood as the germline control when necessary.

7.1.1.3 Tobacco and alcohol use history

A detailed tobacco and alcohol use history will be documented in the patient's chart.

7.1.1.4 Prior Oral Cancer History

The prior oral cancer history will be documented in the patient's chart.

7.1.1.5 Inclusion/Exclusion Criteria

All inclusion and exclusion criteria will be reviewed by the investigator or qualified designee to ensure that the subject qualifies for randomization.

7.1.1.6 Demographics and Medical History

A medical history will be obtained by the investigator or qualified designee. Details regarding the disease for which the subject has enrolled in this study will be recorded in the electronic medical record.

7.1.1.7 Concomitant Medications Review

Concomitant medications will be documented in the electronic medical record so that the information is available for post-hoc analysis of outcomes related to the study, if relevant. Concomitant medications will not be captured in the electronic trial database.

7.1.1.8 Oral Cancer-Free Survival Status

Information on time to development of oral cancer/disease progression/recurrence, sites of disease, development of second primary tumors, additional therapy, long-term survival, and other relevant clinical data may be obtained throughout and after the study period as deemed necessary by the Principal Investigator for trial data interpretation. Patients (or their family members or designees) may be contacted by telephone or in writing or by electronic mail or during clinic visits during or after treatment discontinuation for collection of oral cancersurvival status. The information may also be obtained through chart reviews.

7.1.2.1 Adverse Event (AE) Monitoring

7.1.2 Clinical Procedures/Assessments

The investigator or qualified designee will be responsible for assigning attribution of adverse events to the study drug. The investigator or qualified designee will assess each subject to evaluate for potential new or worsening AEs as specified in the Trial Flow Chart and more frequently if clinically indicated. Adverse experiences will be graded and recorded according to NCI CTCAE Version 4.0 (see Section 7.2)Toxicities will be characterized in terms regarding seriousness, causality, toxicity grading, and action taken with regard to trial treatment.

For subjects receiving treatment with pembrolizumab AEs of unknown etiology associated with pembrolizumab exposure should be evaluated to determine if it is possibly an event of clinical interest (ECI) of a potentially immunologic etiology (termed immune-related adverse events, or irAEs); see the separate ECI guidance document in the Appendix regarding the identification, evaluation and management of potential irAEs.

Please refer to section 7.2 for detailed information regarding the assessment and recording of AEs.

7.1.2.2 Physical Exam

The investigator or qualified designee will perform a physical exam including at least an examination of the oral cavity. Vital signs will be recorded in the patient's chart.

7.1.2.3 Eastern Cooperative Oncology Group (ECOG) Performance Scale

The investigator or qualified designee will assess ECOG status (see Section 11.1) as specified in the Trial Flow Chart.

7.1.3 Laboratory Procedures/Assessments

Details regarding specific laboratory procedures/assessments to be performed in this trial are provided below - Laboratory Safety Evaluations (Hematology, Chemistry).

Laboratory tests for hematology, chemistry, urinalysis, and others are specified in Table 5.

Laboratory tests for Main Study Screening (Visit 2) should be performed within 28 days prior to the first dose of treatment. After Cycle 1, pre-dose laboratory procedures can be conducted up to 72 hours prior to dosing. Results must be reviewed by the investigator or qualified designee and found to be acceptable prior to each dose of trial treatment.

Table 5 Laboratory Tests

Hematology	Chemistry	Urinalysis	Other
Hematocrit	Albumin	Urine pregnancy test †	Serum β-human chorionic gonadotropin†
Hemoglobin	Alkaline phosphatase	Urinalysis	(β-hCG)†
Platelet count	Alanine aminotransferase (ALT)		Total thriiodothyronine (T3)
WBC (total and differential)	Aspartate aminotransferase (AST)		Free tyroxine (T4)
Red Blood Cell Count	Lactate dehydrogenase (LDH)		
Absolute Neutrophil Count	Carbon Dioxide ‡		
Absolute Lymphocyte Count	(CO ₂ or biocarbonate)		
	Uric Acid		
	Calcium		
	Chloride		
	Glucose		
	Phosphorus		
	Potassium		
	Sodium		
	Magnesium		
	Total Bilirubin		
	Direct Bilirubin (If total bilirubin is elevated above the upper limit of normal)		
	Total protein		
	Blood Urea Nitrogen		

[†] Perform on women of childbearing potential only. If urine pregnancy results cannot be confirmed as negative, a serum pregnancy test will be required.

[‡] If considered standard of care in your region.

7.1.4 Non-invasive Efficacy Measurements

7.1.4.1 Oral lesion measurements

Bi-dimensional measurements of visible oral lesions will be recorded in the patient's chart for assessment of clinical response to treatment (a secondary objective of this study). If no visible oral lesions are present, this will also be recorded in the patient's chart.

7.1.5 Tumor Biopsies/Archival Tissue Collection/Correlative Studies Blood and Oral Swabs

Biospecimens collected (including archival and newly obtained oral tissue, blood, oral swab, and invasive cancer specimens) will be used for LOH evaluation, evaluation of histological response to treatment (a secondary objective of the study), as well as correlative studies. As part of the study, a biospecimen repository will be created. The objective of this repository will be to provide material for future evaluations of other relevant biomarkers that may be associated with clinical outcomes. A written informed consent will be obtained from patients enrolled in this study so that these samples may be analyzed in the future for biomarkers not described in this protocol.

Because the population randomized on this study is considered high risk, oral biopsies performed at baseline, months 3 and 12 are considered standard of care for monitoring for histological progression and invasive cancer development.

Biospecimen collection and handling are described in the Appendix.

The correlative studies to be evaluated in the biospecimens include (but are not limited to):

- expression of PD-L1, PD-L2, B7-H3, B7-x/H4, PD-1, LAG-3, 2B4, BTLA, Tim3 in neoplastic cells, immune cells and epithelium
- expression of CD3, CD4, FoxP3, CD8, CD68, CD57, CD45RO in immune cells
- T cell receptor profiling by massive parallel sequencing, and/or T cell receptor expression assay (DTEA)
- whole exome sequencing to determine presence of neo-antigens
- oral microbiome characterization
- genomic analysis (including genome sequencing and SNP analysis)
- proteomic analysis
- phosphorylation status of multiple kinases (using antibody arrays when appropriate)

- non-coding-RNA and messenger-RNA levels, including the expression signatures interferon gamma, TCR signaling, expanded-immune, de novo.
- identification of sub-populations of T-cells (e.g. CD4+ helper T-cells, CD8+ cytotoxic T-cells, CD4+ CD25+ regulatory T-cells, FOXP3) and myeloid derived suppressor cells (CD19-, CD3-, CD14-, HLADR-, CD11b+, CD33+, CD45+) as well as immune phenotypic markers including ICOS/ICOSL; OX40/OX40-L; 41BB/41BB-L; PD-1/PD-L1 and PD-L2; CD69, and HLA-DR (activation markers that affect T cell function)
- Cytokine profiling
- Pembrolizumab serum levels and anti-pembrolizumab antibodies
- Other biomarkers that may emerge to be important related to the biology of oral IEN and/or pembrolizumab therapy

7.2 Assessing and Recording Adverse Events

7.2.1 Serious Adverse Event Reporting (SAE) Reporting

An adverse event or suspected adverse reaction is considered "serious" if, in the view of either the investigator or the IND Office, it results in any of the following outcomes:

- Death
- A life-threatening adverse drug experience any adverse experience that places the patient, in the view of the initial reporter, at immediate risk of death from the adverse experience as it occurred. It does not include an adverse experience that, had it occurred in a more severe form, might have caused death.
- Inpatient hospitalization or prolongation of existing hospitalization
- A persistent or significant incapacity or substantial disruption of the ability to conduct normal life functions.
- A congenital anomaly/birth defect.

Important medical events that may not result in death, be life-threatening, or require hospitalization may be considered a serious adverse drug experience when, based upon appropriate medical judgment, they may jeopardize the patient or subject and may require medical or surgical intervention to prevent one of the outcomes listed in this definition. Examples of such medical events include allergic bronchospasm requiring intensive treatment in an emergency room or at home, blood dyscrasias or convulsions that do not result in inpatient hospitalization, or the development of drug dependency or drug abuse (21 CFR 312.32).

• Important medical events as defined above, may also be considered serious adverse events. Any important medical event can and should be reported as an SAE if deemed appropriate by the Principal Investigator, IND Office, and Merck.

- All events occurring during the conduct of a protocol and meeting the definition of a SAE must be reported to the IRB in accordance with the timeframes and procedures outlined in "The University of Texas M. D. Anderson Cancer Center Institutional Review Board Policy for Investigators on Reporting Serious Unanticipated Adverse Events for Drugs and Devices". Unless stated otherwise in the protocol, all SAEs, expected or unexpected, must be reported to the IND Office, regardless of attribution (within 5 working days of knowledge of the event).
- All life-threatening or fatal events, that are unexpected, and related to the study drug, must have a written report submitted within 24 hours (next working day) of knowledge of the event to the Safety Project Manager in the IND Office.
- Unless otherwise noted, the electronic SAE application (eSAE) will be utilized for safety reporting to the IND Office and MDACC IRB.
- Serious adverse events will be captured from the time of the first protocol-specific intervention, until 30 days after the last dose of drug, unless the participant withdraws consent. Serious adverse events must be followed until clinical recovery is complete and laboratory tests have returned to baseline, progression of the event has stabilized, or there has been acceptable resolution of the event.
- Additionally, any serious adverse events that occur after the 30 day time period that are related to the study treatment must be reported to the IND Office. This may include the development of a secondary malignancy.

7.2.1.1 Reporting to FDA:

• Serious adverse events will be forwarded to FDA by the IND Office (Safety Project Manager IND Office) according to 21 CFR 312.32.

It is the responsibility of the PI and the research team to ensure serious adverse events are reported according to the Code of Federal Regulations, Good Clinical Practices, the protocol guidelines, the Merck's guidelines, and Institutional Review Board policy.

Changes resulting from normal growth and development that do not vary significantly in frequency or severity from expected levels are not to be considered adverse events. Examples of this may include, but are not limited to, teething, typical crying in infants and children and onset of menses or menopause occurring at a physiologically appropriate time.

Merck product includes any pharmaceutical product, biological product, device, diagnostic agent or protocol-specified procedure, whether investigational (including placebo or active comparator medication) or marketed, manufactured by, licensed by, provided by or distributed by Merck for human use.

Adverse events may occur during the course of the use of Merck product in clinical trials or within the follow-up period specified by the protocol, or prescribed in clinical practice, from overdose (whether accidental or intentional), from abuse and from withdrawal.

Adverse events may also occur in screened subjects during any pre-allocation baseline period as a result of a protocol-specified intervention, including washout or discontinuation of usual therapy, diet, placebo treatment or a procedure.

Development of oral cancer is not considered an adverse event unless it is considered to be drug related by the investigator.

For the purpose of this study, adverse events that in the opinion of the treating investigator are related to planned procedures (e.g., usual pain, usual bleeding, intra- or post-procedure electrolyte imbalances and other clinically insignificant laboratory abnormalities) will not be captured and/or reported.

Adverse events will only be recorded for patients that undergo randomization. Adverse events will be recorded from the time the patient is randomized through the end of treatment / reevaluation visit (month 3) or 90 days following cessation of treatment, whichever is longer.

Any new serious adverse event that occurs more than 30 days after last study drug administration should be reported if considered related to study drug (e.g., secondary cancer). Should a patient discontinue from or complete the study and commence subsequent anticancer therapy within 30 days of the last study drug administration, adverse events attributable to this subsequent therapy should not be recorded.

Laboratory abnormalities are usually not recorded as adverse events; however, signs and/or symptoms that are associated with laboratory findings requiring study withdrawal, dose modification, or medical intervention (e.g., anemia requiring transfusions or hyperglycemia requiring treatment) or other abnormal assessments (e.g., ECG, radiographs, vital signs) must be recorded as adverse events (or serious adverse events) if they meet the definition of an adverse event (or serious adverse event). In addition, laboratory abnormalities marked as clinically significant should also be recorded as adverse events. The investigator will report the most severe grade of the clinically significant laboratory abnormality and will evaluate its relationship to the study drug and clinical condition.

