7.3.1. Immediate Reporting Serious Adverse Events to Merck

A serious adverse event is any adverse event occurring at any dose or during any use of Merck's product that:

- Results in death;
- Is life threatening;
- Results in persistent or significant disability/incapacity;
- Results in or prolongs an existing inpatient hospitalization;
- Is a congenital anomaly/birth defect;
- Is a new cancer (that is not a condition of the study);
- Is associated with an overdose;
- Is another important medical event

Refer to Table 6 for additional details regarding each of the above criteria.

Any serious adverse event, or follow up to a serious adverse event, including death due to any cause other than progression of the cancer under study that occurs to any subject from the time the subject is randomized through 90 days following cessation of treatment, or the initiation of new anti-cancer therapy, whichever is earlier, whether or not related to Merck product, must be reported within 5 working days of knowledge of the event to the IND Office and within 2 working days to Merck Global Safety.

ECIs (both non-serious and serious adverse events) identified in this guidance document from the date of first dose through 90 days following cessation of treatment, or 30 days after the initiation of a new anticancer therapy, whichever is earlier, need to be reported within 24 hours to the IND Office and within 2 working days to Merck Global Safety(Attn: Worldwide Product Safety; [contact]), regardless of attribution to study treatment, consistent with standard SAE reporting guidelines.

Non-serious Events of Clinical Interest will be forwarded to Merck Global Safety and will be handled in the same manner as SAEs.

Additionally, any serious adverse event, considered by an investigator who is a qualified physician to be related to Merck product that is brought to the attention of the investigator at any time outside of the time period specified in the previous paragraph also must be reported immediately to the IND Office and to Merck.

All subjects with serious adverse events must be followed up for outcome.

Product: MK-3475

Protocol/Amendment No.:

Table 6 Evaluating Adverse Events

An investigator who is a qualified physician, will evaluate all adverse events as to:

V4.0 CTCAE Grading	Grade 1	Mild; asymptomatic or mid symptoms; clinical or diagnostic observations only; intervention not indicated.		

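### Unrelated SAEs on days 31 to 90 after the last dose fall under conflicting reporting rules, and no AE review is scheduled after month 3 although AE recording runs to 90 days after treatment stops

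*Combined protocol and SAP*

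**What the plan says.** **SAE reporting.** Section 7.2.1 gives a general rule: "Unless stated otherwise in the protocol, all SAEs, expected or unexpected, must be reported to the IND Office, regardless of attribution", within 5 working days. It then sets a period: "Serious adverse events will be captured from the time of the first protocol-specific intervention, until 30 days after the last dose of drug". For later events it says that "serious adverse events that occur after the 30 day time period that are related to the study treatment must be reported" to the IND Office. Further down, under the FDA-reporting subheading, it repeats the condition: "Any new serious adverse event that occurs more than 30 days after last study drug administration should be reported if considered related to study drug".

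Section 7.3.1 sets a different period for SAEs: "from the time the subject is randomized through 90 days following cessation of treatment, or the initiation of new anti-cancer therapy, whichever is earlier". Such an event, "whether or not related to Merck product, must be reported within 5 working days of knowledge of the event to the IND Office", and also goes to Merck within 2 working days. Events of clinical interest (ECIs) have their own rule in the same section. They are reportable from the first dose through 90 days after cessation, or 30 days after new anti-cancer therapy if earlier, "regardless of attribution to study treatment, consistent with standard SAE reporting guidelines".

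**AE recording and review.** Section 7.2.1 records AEs in randomized patients from randomization "through the end of treatment / reevaluation visit (month 3) or 90 days following cessation of treatment, whichever is longer". In the flow chart (section 6.2), the AE-review row is marked at screening, cycles 2 to 4 and month 3, and in no later column. Section 7.1.2.1 ties AE assessment to that chart and allows more frequent assessment when clinically indicated. Section 5.2.1.2 warns that immune-related events can appear months after dosing ends.

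**Analysis.** Section 8.3 summarizes toxicity in frequency tables for everyone who received treatment. It does not say which time window the tables cover.

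**The concern.** There are two separate problems.

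First, the SAE rules disagree on how long unrelated events must be reported. Staff who work from the 30-day sentence in section 7.2.1 would not report an unrelated hospitalization on day 60, which section 7.3.1 requires.

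Second, the plan promises AE recording well beyond the last visit at which anyone is scheduled to ask about AEs. Treatment is an immune checkpoint inhibitor, and the protocol itself expects late events. Safety and tolerability is a secondary objective (section 3.3). If late events are collected only when a patient happens to mention them, the toxicity tables may be incomplete for the later part of the window, and section 8.3 does not tell a reader what window was intended.

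**Working it through.** **Part 1: the SAE rules side by side.** The plan gives no figure to reproduce here, so the check compares the text.

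| Item | Section 7.2.1 | Section 7.3.1 |
|---|---|---|
| Start | First protocol-specific intervention | Randomization |
| End | 30 days after last dose | 90 days after cessation, or new anti-cancer therapy if earlier |
| After day 30 | Related SAEs | All SAEs to day 90; related SAEs after that |
| Recipient | IND Office | IND Office and Merck |

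- The difference is not one rule per recipient, because both sections name the IND Office.
- The general rule in section 7.2.1 does not decide the matter. It yields wherever the protocol says otherwise, and the 30-day sentences can be read as saying otherwise.
- Related SAEs after day 30 are reportable under both sections. The conflict is confined to SAEs judged unrelated on days 31 to 90: 90 − 31 + 1 = 60 days, or fewer if new anti-cancer therapy starts sooner.
- This is a reporting problem and does not in itself change the toxicity rate. Section 7.2.1 already records any AE in randomized patients to day 90, section 7.2.4 has each one assessed for seriousness, and section 8.3 analyzes treated patients only.

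**Part 2: days in the AE window after the last scheduled review.**

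Inputs: four doses, one every 3 weeks (Table 2); dose window ±7 days (section 5.2.2); month 3 visit ±7 days (flow chart); after a treatment delay, that visit is at least 2 weeks after the last dose (flow-chart footnote c). Assumption: month 3 means day 85 (12 weeks) to day 92 (calendar months).

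Formula: gap = 90 − (day of month 3 visit − day of last dose).

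1. Nominal doses fall on days 1, 22, 43 and 64. The visit is 85 − 64 = 21 to 92 − 64 = 28 days after the last dose. Gap: 90 − 28 = 62 to 90 − 21 = 69 days (62/90 = 69% to 69/90 = 77%).
2. With the visit window alone around day 92 (days 85 to 99), the visit is 21 to 35 days after the last dose. Gap: 55 to 69 days.
3. With both windows, the last dose falls on days 57 to 71 and the visit on days 78 to 99. The longest interval is 99 − 57 = 42 days. The shortest is taken as 14 days, from footnote c. Gap: 90 − 42 = 48 to 90 − 14 = 76 days (53% to 84%).
4. Early stopping, nominal dates:

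| Doses received | Last dose (day) | Last dose to visit (days) | Gap (days) |
|---|---|---|---|
| 3 | 43 | 42–49 | 41–48 |
| 2 | 22 | 63–70 | 20–27 |
| 1 | 1 | 84–91 | 0–6 |

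**Could the first post-treatment visit close the gap?** After four nominal doses the recording window closes on day 64 + 90 = 154 (147 to 161 with the dose window). The month label of the first post-treatment visit cannot be read in the available text. The third post-treatment column carries the tissue collection that section 7.1.5 places at month 12, so the first visit lies between months 3 and 12. Assumed range, with the ±1 month visit window:

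- month 4: about days 92 to 153, inside the recording window;
- month 5: about days 123 to 184, straddling its close;
- month 6: about days 153 to 214, essentially at or after its close.

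**The case against.** **On reporting.** No sentence forbids reporting unrelated SAEs after day 30. A team that reported everything to day 90 and related SAEs thereafter would breach nothing, and section 7.2.1 also tells the team to follow Merck's guidelines. This is a single-institution trial, so sites cannot diverge. Part of this stands: a cautious team can comply with both sections. But no text says that the rules add up or that the stricter one governs, and on that reading the 30-day limit and the relatedness condition would have no purpose. Staff at one center can still follow the wrong sentence. The difference in start points is the lesser part of this problem.

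**On ascertainment.** The safeguards are real. Related SAEs have no end date, and ECIs are reportable to day 90 regardless of attribution. Unscheduled assessment is allowed. Physical examinations continue after month 3, and at the first post-treatment visit the experimental arm has blood count, chemistry and thyroid tests. Clinically significant laboratory abnormalities are to be recorded as AEs (section 7.2.1). These safeguards limit the risk but do not remove it. The examination need only cover the oral cavity (section 7.1.2.2), ECI assessment is scheduled only before each dose (section 7.2.3), and unscheduled assessment depends on someone raising the event.

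**On precision.** The day counts depend on how month 3 is read. The 76-day limit applies the 14-day minimum, which footnote c gives only for delayed patients; without it, the windows alone would allow 78 − 71 = 7 days and a gap of 83. The counts measure days without a scheduled review, not missed events. The flow chart is also imperfectly reproduced, although its AE-review row shows no mark after month 3. These points stand as limits on the figures, not as answers to the problem.

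**Conclusion.** Both parts hold. The SAE rules in sections 7.2.1 and 7.3.1 conflict for events judged unrelated on days 31 to 90 after the last dose, and they start at different points. The AE recording window outlasts the scheduled reviews by about 62 to 69 of 90 days after four on-time doses, and by about 48 to 76 days under the windows and the 14-day minimum used above. The gap is smaller after early stopping. These figures assume that month 3 means day 85 to 92.

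The consequences are limited. The reporting conflict leaves the toxicity rate unchanged, and the ascertainment gap mainly threatens late AEs that are non-serious or not volunteered. The documents give no distribution of onset times, so the effect on the toxicity tables cannot be estimated. The change should be made because it is cheap and removes an ambiguity in safety reporting.

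**What to change.** 1. Reconcile sections 7.2.1 and 7.3.1 to one start point, one end point and one attribution rule for SAEs. The choice of window is the sponsor's.
2. Add an AE review, with onset dates, at the first post-treatment visit in the flow chart, where safety laboratory tests are already marked for the experimental arm.
3. State in section 8.3 that the toxicity tables use the AE recording window of section 7.2.1, with later events listed separately.

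The cost is protocol wording, one flow-chart mark at a visit that already takes place, one sentence in section 8.3, and slightly more event recording. If the visit falls after the recording window closes, the added review is partly retrospective. Onset dates are needed so that events can still be assigned to the right window.
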